9.8. Prior and Concomitant Medications

Prior and concomitant medications will be coded using the latest World Health Organization (WHO) Drug Dictionary March 2023 Global B3 version or later.

Prior medications are defined as any medications, other than study drug, with a stop date before the first dose of study drug.

Concomitant medications are medications, other than study drug, being taken on or after the first study drug dose date and up to 30 days after the date of the last study drug dose. Medications that started before the first dose of study drug and were ongoing on the date of the first dose of study drug will be considered as both prior and concomitant medications. Prior and concomitant medications will be summarized by the WHO Drug Dictionary Anatomical Therapeutic Chemical 2nd level (ATC-2) and preferred name, for the SAF. If the ATC-2 level term is not available, the next available level (e.g., ATC-1) will be used. The numbers and percentages of participants who received the medications will be tabulated. A participant who takes more than one medication will be counted only once if these medications belong to the same extended ATC classification.

Prior and concomitant medications will be listed for the SAF.

Narcotic analgesic medication will be included in the prior and concomitant medications, but specific usage will be collected in participant diary. Diary data will be listed for the SAF.

9.9. Medical History

Medical history will be coded using the MedDRA version 26.0 or higher.

The frequency and percentage of participants experiencing any medical conditions will be tabulated by SOC and PT. If a PT or SOC was reported more than once for a participant, the participant will only be counted once in the incidence for that PT or SOC.

Medical history data will be listed for the SAF.

9.10. Efficacy Analyses

Results for endpoints based on assessment by the IRR (RECIST v1.1, mRECIST and TVS) will be obtained through review by two independent radiologists and adjudication as needed. Analyses of IRR results will be based on the assessments of reviewer number 1 (assigned independently by the IRR vendor), unless reviewer number 2 was selected through the adjudication process performed by the IRR vendor. This process is described in an Independent Review Charter.

9.10.1. Multiplicity Control

To control overall type I error, a hierarchical testing procedure will be utilized. Statistical testing will be performed for the analysis of primary and key secondary endpoints in the following order at a 2-sided 0.05 alpha level for each:

- 1. ORR per RECIST v1.1 at Week 25
- 2. ORR per TVS at Week 25
- 3. Mean change from baseline in active ROM at Week 25
- 4. Mean change from baseline in the PROMIS-physical function score at Week 25
- 5. Mean change from baseline in the worst stiffness NRS score at Week 25
- 6. Mean change from baseline in EQ-VAS at Week 25
- 7. Proportion of responders based on BPI-30 (worst pain) NRS score and narcotic analgesic use at Week 25

If the primary endpoint is not statistically significantly different between treatment groups, the secondary endpoints will not be formally tested and nominal p-values will be provided. Contingent upon significance in the primary endpoint, each of the secondary efficacy endpoints will be tested sequentially in the order above. If any of the endpoints are not statistically significantly different between treatment groups, all subsequent endpoints will not be formally tested and nominal p-values will be provided.

9.10.2. Primary Endpoint

Objective response rate (ORR) per RECIST v1.1 at Week 25 is defined as the proportion of participants with a CR or a PR as the Week 25 Tumor Response (as defined in Table 2) based on IRR per RECIST v1.1. ORR at Week 25 will be compared between the 2 treatment groups using a two-sided Cochran-Mantel-Haenszel (CMH) test stratified by the randomization stratification factors. The test will be performed at a 0.05 alpha level on the ITT Set. A 95% CI for the proportion in each arm using the Clopper-Pearson method as well as the difference in proportion and its associated Wald 95% CI will be presented. A Fisher's exact test and an exact 95% CI for the difference in proportion will be provided as a sensitivity analysis.

No confirmation (ie, CR or PR at the subsequent MRI assessment) will be required for a CR or PR per RECIST v1.1 as this is a randomized study. Complete and partial response will define response for the primary endpoint and additional efficacy analyses.

Determination of an overall response for each timepoint is based on the combination of responses for target lesions, and the presence or absence of one or more new lesions per RECIST v1.1. For this study, determination of the tumor response status for each participant in Part 1 with respect to the primary efficacy endpoint is shown in Table 2 below. All unscheduled assessments prior to Week 25 will be incorporated into the determination of ORR at Week 25 in a similar fashion as Week 13. End of Part 1 scans will be windowed according to Section 8.3. If a participant is missing a scan at Week 25, then they will be considered a non-responder.

Table 2: Definitions of Response for the Primary Efficacy Endpoint

Timepoint Response at Week 13	Timepoint Response at Week 25	End of Part 1 (Week 25) Tumor Response Status
		(Primary Efficacy Endpoint)
CR or PR	CR	Response (CR)
CR or PR	PD	Non-response (PD)
PR	Non-CR/non-PD/non-NE ^a	Response (PR) ^b
SD	CR or PR	Response (CR or PR)
SD	SD	Non-response (SD)
SD	PD	Non-response (PD) ^c
CR, PR, SD, and NE	NE	Non-response (NE)
PD	Any	Non-response (PD)
NE	CR or PR	Response (CR or PR)
NE	SD or PD	Non-response (SD or PD)

Abbreviations: CR=complete response; NE=not evaluated or unevaluable; PD=progressive disease; PR=partial response; SD=stable disease.

A forest plot summarizing the difference in ORR at Week 25 between vimseltinib and placebo and its associated Wald 95% CI will be generated for the subgroups listed in Section 9.10.5 to evaluate the consistency of treatment effects in the subgroups.

A sensitivity analysis will compare the ORR by Week 25 between the 2 treatment groups using the same approach used for the primary endpoint analysis. In this analysis the assignment of response would differ from the approach described in Table 2 in that any participant who met the criteria for response at least once up to, and including, Week 25 would be counted as a responder.

^a Neither sufficient shrinkage to qualify for CR nor sufficient increase to qualify for PD, taking as reference the nadir at Week 13.

^b A tumor that has achieved the criteria of PR will be considered an ongoing PR until progressive disease is objectively documented.

^c To be considered SD, the tumor must achieve the criteria for SD at the Week 25 visit; shorter duration SD will not be considered SD at the End of Part 1.

The analysis may also be performed on the PP Set if the proportion of participants from the ITT Set who are excluded from PP Set exceeds 5%.

Response data by IRR, including the at Week 25 derived response, will be presented in by-participant listings.

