12.4.5. Efficacy Analyses

12.4.5.1. Primary Efficacy Analysis

Objective response rate is defined as the proportion of participants with a CR or a PR based on IRR per RECIST v1.1. Objective response rate at Week 25 will be compared between the 2 treatment arms using a two-sided Cochran-Mantel-Haenszel test stratified by the randomization stratification factors. The test will be performed at a 0.05 alpha level on the ITT set. A 95% CI for the proportion in each arm and for the difference in proportion will be presented.

No confirmation (ie, CR or PR at the subsequent MRI assessment) will be required for a CR or PR per RECIST v1.1 for a randomized study. Complete and partial response will define response for the primary endpoint and additional efficacy analyses.

Determination of an overall response for each timepoint is based on the combination of responses for target lesions, and the presence or absence of one or more new lesions. For this protocol, determination of the tumor response status for each participant in Part 1 with respect to the primary efficacy endpoint is shown in Table 18.

Response at Week 13	Response at Week 25	End of Part 1 Tumor Response Status (Primary Efficacy Endpoint)
CR or PR	CR	Response (CR)
CR or PR	PD	Non-response (PD)
PR	Non-CR/non-PD/non-NE ^a	Response (PR) ^b
SD	CR or PR	Response (CR or PR)
SD	SD	Non-response (SD)
SD	PD	Non-response (PD) ^c
CR, PR, SD, and NE	NE	Non-response (NE)

 Table 18:
 Definitions of Response for the Primary Efficacy Endpoint

Response at Week 13	Response at Week 25	End of Part 1 Tumor Response Status (Primary Efficacy Endpoint)
PD	Any	Non-response (PD)
NE	CR or PR	Response (CR or PR)
NE	SD or PD	Non-response (SD or PD)

Abbreviations: CR=complete response; NE=not evaluated or inevaluable; PD=progressive disease; PR=partial response; SD=stable disease.

^a Neither sufficient shrinkage to qualify for CR nor sufficient increase to qualify for PD, taking as reference the nadir at Week 13.

^b A tumor that has achieved the criteria of PR will be considered an ongoing PR until progressive disease is objectively documented.

^c To be considered SD, the tumor must achieve the criteria for SD at the Week 25 visit; shorter duration SD will not be considered SD at the End of Part 1.

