6. RANDOMIZATION AND BLINDING

The study will randomize approximately 120 participants with TGCT in a 2:1 ratio (vimseltinib:placebo). Randomization will be stratified for tumor location (lower limb vs. all other) and region (U.S. vs. non-U.S.).

The present document, a comprehensive statistical analysis plan (SAP), will be approved by the Sponsor prior to the unblinding of study data.

Where required, safety personnel at the Sponsor or designee may be unblinded to a participant's study drug assignment to meet reporting requirements to regulatory agencies. In addition, the Investigator, participant, Sponsor, and study team will be unblinded at the time the participant has disease progression by RECIST v1.1 based on IRR.

Additional Sponsor representatives may be unblinded to some data for the purposes of ensuring adequacy of study conduct, including proper distribution of study drug.

At no point in time before official full study unblinding for the primary analysis will any aggregate efficacy and safety analyses by true treatment assignment be conducted by the Sponsor or Sponsor representatives, unless there is explicit permission to do so, for instance high level efficacy assessment for the purposes of a data monitoring committee (DMC) review to determine the adequacy of the risk/benefit profile of the drug as it pertains to the conduct of the clinical study.

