BPI-30 response at Week 25 will be compared between the 2 treatment groups using the same approach used for the primary endpoint analysis. A summary of narcotic use over time will be provided.

A forest plot summarizing the unstratified 95% CI of the difference in BPI response rate at Week 25 between vimseltinib and placebo will be generated for the subgroups listed in Section 9.10.5 to evaluate the consistency of treatment effects in the subgroups.

All BPI data will be presented in by-participant listings.

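### The binary endpoints are decided by a stratified CMH test, but the difference and Wald interval reported beside it use no strata on their plain reading, so test and interval need not agree

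*SAP*

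**What the plan says.** Randomization uses two binary factors, giving four strata (SAP 6): "Randomization will be stratified for tumor location (lower limb vs. all other) and region (U.S. vs. non-U.S". The primary test uses those factors (SAP 9.10.2): "using a two-sided Cochran-Mantel-Haenszel (CMH) test stratified by the randomization stratification factors". It is the deciding test: "The test will be performed at a 0.05 alpha level on the ITT Set".

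The same section then promises Clopper-Pearson intervals per arm "as well as the difference in proportion and its associated Wald 95% CI will be presented". The only other comparison of arms there by a different method is unstratified in kind: "A Fisher's exact test and an exact 95% CI for the difference in proportion will be provided as a sensitivity analysis". Protocol 12.4.5.1 names no method: "A 95% CI for the proportion in each arm and for the difference in proportion will be presented".

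The arrangement is inherited. SAP 9.10.3.6: "BPI-30 response at Week 25 will be compared between the 2 treatment groups using the same approach used for the primary endpoint analysis". SAP 9.10.3.1 (TVS ORR) and 9.10.4.2 (mRECIST ORR) also refer back to the primary method. TVS ORR and BPI-30 are steps 2 and 7 of the testing hierarchy in SAP 9.10.1. The continuous key secondary endpoints differ: their MMRM in SAP 9.10.3 adjusts for region and for tumor location (joint type for ROM).

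**The concern.** A reader expects the effect estimate and interval printed beside a p-value to answer the same question as the p-value. Here the p-value conditions on the strata and uses a variance computed under no difference. The interval, as written, ignores the strata and uses an unpooled variance. These are two separate sources of mismatch, and they pull in opposite directions. At stake is the accuracy and coherence of the reported effect size for four endpoints, two of them in the hierarchy after the primary. An awkward case would be an interval clear of zero beside a CMH test that has failed and stopped the sequence.

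**Working it through.** **Inputs from the documents.** 80 vs 40 participants, 35% vs 5%, two-sided 5% (SAP 5); 2 × 2 strata (SAP 6); CMH test and Wald interval (SAP 9.10.2). The documents give no stratum sizes, no stratum response rates and no BPI-30 rates. Everything that depends on these is assumed below and shown over a range.

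**1. The plan's own figure.** Enumerating both binomials at 80/40 with the two-sided Fisher test gives 98.3% power, against 98% stated. It reproduces, and nothing below alters it.

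**2. Simple Wald interval at the expected counts, 28/80 vs 2/40.** SE = √(0.35×0.65/80 + 0.05×0.95/40) = √(0.002844 + 0.001188) = 0.0635. The interval is 30.0 ± 12.4 points, or 17.6 to 42.4.

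**3. Effect of ignoring the strata.** With equal strata, p(1−p) = mean of p_k(1−p_k) + variance of p_k between strata. Stratified allocation removes the second term from the sampling variance; the simple formula keeps it. The excess variance is V1/80 + V0/40, where V1 and V0 are the between-stratum variances in the two arms. The moderate, strong and extreme rows assume two equal strata and keep 35% vs 5% overall. The row with no effect used four strata (60/20/10/10%). Simulated values come from 40,000 trials each; mean SE is the mean half-width divided by 1.96.

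| Assumed stratum rates | V1/80 + V0/40 | True SE by formula | Simulated mean Wald SE | Simulated SD | Coverage |
|---|---|---|---|---|---|
| No prognostic effect | 0 | 0.0635 | 0.0627 | 0.0635 | 94.6% |
| Moderate: 25/45%, 3/7% | 0.000135 | 0.0624 | 0.0627 | 0.0624 | 95.0% |
| Strong: 15/55%, 0/10% | 0.000563 | 0.0589 | 0.0628 | 0.0590 | 96.2% |
| Extreme: 5/65%, 0/10% | 0.001188 | 0.0533 | 0.0628 | 0.0535 | 97.9% |

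The Wald SE is therefore about 1% too small with no prognostic effect, right under moderate prognosis, 6% too large under strong and 17% under extreme.

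Four equal strata with strongly differing rates give 0.0627 against 0.0595 at 35% vs 5% (5% too large). With no treatment difference and rates of 5, 20, 40 and 60% in both arms, the simple variance is 0.3125×0.6875×0.0375 (SE 0.0898) and the true one 0.1719×0.0375 (SE 0.0803). Simulation gives 0.0889 against 0.0804, 11% too large, and the nominal 95% interval excludes zero in only 3.3% of trials.

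**4. Effect of the unpooled variance.** CMH uses the variance under no difference. At 35% vs 5% the pooled rate is 30/120 = 0.25, so that SE is √(0.25×0.75×0.0375) = 0.0839, against 0.0635 unpooled. The Wald interval therefore excludes zero more readily than CMH rejects. Share of simulated trials where Wald excludes zero but CMH does not reject:

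- 35% vs 5%, no prognostic effect: 0.7%
- 40% vs 22%, no prognostic effect: about 5%
- 20% vs 5%, two strata (10/30%, 2/8%): 10.5%
- 18% vs 5%, no prognostic effect: 14.7%

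**5. One data set as illustration.** Take four strata of 20 vs 10, with responders 4, 4, 3, 3 on vimseltinib and 1, 1, 0, 0 on placebo (14/80 vs 2/40).

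- Wald: 12.5 ± 1.96×√(0.175×0.825/80 + 0.05×0.95/40) = 12.5 ± 10.7, or 1.8 to 23.2 points. It excludes zero.
- CMH: the stratum excesses are 0.667, 0.667, 1 and 1, summing to 3.333. The variances are m(30−m)/130.5 with m = 5, 5, 3, 3, summing to 3.157. Chi-square = 3.333²/3.157 = 3.52, p = 0.061. Not significant.
- Stratified Miettinen-Nurminen with Mantel-Haenszel weights, solved numerically: −0.7 to 23.5 points. It includes zero, as CMH requires.

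**6. Why that interval always agrees.** With weight w = n1·n0/N in each stratum, the numerator at zero difference is w(x1/n1 − x0/n0) = x1 − n1·m/N, which is the CMH numerator. The score variance with the N/(N−1) factor is w²·p(1−p)·(1/n1 + 1/n0)·N/(N−1) = n1·n0·p(1−p)/(N−1), with p = m/N. That equals the CMH variance n1·n0·m(N−m)/[N²(N−1)]. The two statistics are identical at zero, and 200,000 simulated trials in each of six scenarios showed no disagreement.

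**The case against.** **The interval decides nothing.** SAP 9.10.1 runs on significance, and CMH is the named test. BPI-30, where disagreement is more plausible, is last and gates nothing. This stands, and it limits the point to reporting.

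**The text does not say unstratified.** SAP 9.10.2 says only "difference in proportion and its associated Wald 95% CI will be presented". For the key secondary subgroup plots the SAP does state when an interval is unstratified or unadjusted. A reader might infer that the plan openly chose an unstratified primary interval; the documents support only that this is the plain reading. If a stratified interval was meant, its estimator, weights and variance are missing, so an edit is needed either way.

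**The interval is not simply too wide.** A reader might infer this from the missing strata. It requires prognostic strata, and nothing in the documents shows that location or region predicts response. Without prognosis the error is slight and in the other direction, and the conflicts in step 4 come from the unpooled variance, not from stratification. When strata do matter, the interval errs conservatively.

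**The point estimate hardly moves.** With exact 2:1 allocation inside each stratum, the Mantel-Haenszel and simple differences coincide. This stands.

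**Stratifying alone does not bring agreement.** At an assumed 40% vs 22% with strong strata, a stratified Newcombe interval disagreed with CMH in 5.9% of trials and a Mantel-Haenszel interval with Sato variance in 5.3%, against 2.5% for simple Wald. This stands, and it is why the fix names one interval.

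**The plan has a sensitivity analysis.** Fisher's test with an exact interval is there, but it too names no strata, so it does not fill the gap.

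**Conclusion.** The concern holds as a mismatch between the deciding test and the reported interval, for ORR, TVS ORR, BPI-30 and mRECIST ORR. The size is modest. Under strongly prognostic strata the SE is about 5% to 11% too large, reaching 17% only under the extreme assumption. Without prognosis, coverage is about 94% to 95%. A sparse 5% vs 5% case fell to 91.7%. At the design effect, test and interval conflict in under 1% of trials; at an assumed 40% vs 22% without prognosis, in about 5%. Conflict is more frequent at effects well below the design value.

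These sizes rest on assumed stratum sizes and rates and on exact 2:1 balance within strata. A reader might go further and doubt the primary test or the sample size. The documents do not support that: the CMH test is valid for this randomization, its type I error is untouched, and the 98% power reproduces. This is a low-cost improvement worth making, not a flaw that threatens the primary conclusion.

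**What to change.** In SAP 9.10.2, specify as the main effect measure the Mantel-Haenszel-weighted risk difference across the randomization strata, with a stratified Miettinen-Nurminen (score) 95% CI on the same strata as the CMH test. State the weights (n1·n0/N), the N/(N−1) factor and that CMH is run without continuity correction, because exact agreement depends on all three. Add a rule for sparse strata; a stratum with only one arm has weight zero in both the test and the interval. Carry the same wording to TVS ORR, BPI-30 and mRECIST ORR. Keep the simple difference with its Wald interval as supportive, along with the planned Fisher analysis. Do not offer stratified Newcombe as an equivalent option, since it does not track the CMH result.

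The cost is a few lines of SAP text and modest programming, done before unblinding. No new data are needed, and Protocol 12.4.5.1 can stay as it is because it names no interval method.

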5. SAMPLE SIZE DETERMINATION

The sample size selection of approximately 120 participants with TGCT (n~80 vimseltinib, n~40 placebo) was based on considerations for powering the analyses of the primary endpoint, key secondary endpoints, detection of rare safety events and overall exposure to vimseltinib, assuming 15% participant dropout. Participants will be randomized in a 2:1 ratio of vimseltinib versus placebo.

This sample size will have 98% power to detect a statistically significant difference between treatment groups, assuming true ORRs of 35% and 5% in the vimseltinib arm and the placebo arm, respectively, using a two-sided Fisher's exact test at a 5% type I error rate level.

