9.10.3.1. Tumor Response by Tumor Volume Score (TVS)

In addition to being assessed using RECIST v1.1 (primary endpoint), tumor response will also be assessed using TVS. Objective response rate by TVS is defined as the proportion of participants with a CR or PR.

Tumor volume score ORR at Week 25 will be compared between the 2 treatment groups using the same approach used for the primary endpoint analysis. The tumor response status at Week 25 based on TVS will follow the same approach described in Table 2 for the primary endpoint.

Sensitivity analyses similar to the ones planned for the primary endpoint will be performed.

A forest plot summarizing the difference in TVS ORR at Week 25 between vimseltinib and placebo and its associated Wald 95% CI will be generated for the subgroups listed in Section 9.10.5 to evaluate the consistency of treatment effects in the subgroups.

All TVS data will be presented in by-participant listings.

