9.10.5. Sub-group Analyses

The primary efficacy endpoint and key secondary efficacy endpoints will be analyzed in participant subgroups defined as follows:

• Tumor location (lower limb vs all other)

- Region (U.S. vs non-U.S.)
- Participants with disease located in large joints (shoulder, elbow, hip, or knee) vs small joints (joints other than the shoulder, elbow, hip, or knee)
- Participants with disease located in the knee
- Disease subtype (localized vs diffuse)
- Participants at sites in the EU region only
- Age $(18 \le age < 50, 50 \le age < 65, age \ge 65)$
- Gender (female vs male)
- Prior surgery (yes vs no)
- Prior imatinib/nilotinib (yes vs no)

The applicable key secondary efficacy endpoints are TVS, ROM, PROMIS-PF, worst stiffness NRS, EQ-VAS and BPI-30 response.

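### The RECIST and TVS subgroup forest plots prescribe Wald intervals, which give an arm with no responders zero variance, so bars in sparse subgroups can be too narrow or have no width

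*SAP*

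**What the plan says.** SAP 9.10.2 specifies the subgroup display for the primary endpoint: "A forest plot summarizing the difference in ORR at Week 25 between vimseltinib and placebo and its associated Wald 95% CI will be generated". SAP 9.10.3.1 repeats this for tumor volume score: "A forest plot summarizing the difference in TVS ORR at Week 25 between vimseltinib and placebo and its associated Wald 95% CI will be generated". Both sections say that the plots are there to judge whether the treatment effect is consistent across subgroups.

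SAP 9.10.2 also plans Clopper-Pearson intervals for each arm, and adds: "A Fisher's exact test and an exact 95% CI for the difference in proportion will be provided as a sensitivity analysis". That sentence belongs to the overall ITT comparison. SAP 9.10.3.1 promises similar sensitivity analyses for TVS and does not mention subgroups in doing so.

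SAP 9.10.5 lists ten subgroup items, including age 65 or over and prior imatinib/nilotinib. It names no interval method, no rule for arms without responders and no minimum size. Expected subgroup sizes appear nowhere in the protocol or the SAP. For BPI-30, SAP 9.10.3.6 asks for "A forest plot summarizing the unstratified 95% CI of the difference in BPI response rate at Week 25" without naming a method.

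The only planning rates are in SAP 5, for the primary endpoint: "assuming true ORRs of 35% and 5% in the vimseltinib arm and the placebo arm, respectively", with about 80 and 40 participants.

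**The concern.** The Wald interval for a difference estimates each arm's variance from that arm's observed proportion. If an arm has no responders, its estimated variance is zero whatever its size. The plan expects a low placebo response rate and has about 40 placebo participants to divide among subgroups, so a subgroup without a placebo responder is likely.

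Readers judge consistency from how wide the bars are and whether they cross zero. In a sparse subgroup both features can mislead: the lower limit can be too high, the upper limit too low, or the bar can shrink to a point. What is at stake is the reading of a descriptive display, not a test.

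**Working it through.** **Inputs.** From SAP 5: 80 vs 40 participants, 35% vs 5%, two-sided Fisher's exact test at 5%. From SAP 9.10.2 and 9.10.3.1: a Wald 95% CI for the difference, taken here as the usual unpooled form. All subgroup sizes below 80/40, and the 10% vs 5% scenario, are assumptions.

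**The plan's own figure.** Enumerating both binomials with Fisher's exact test at 80/40 gives 98.3% power, so the stated 98% reproduces.

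**How likely is an empty placebo arm?** At a 5% rate the chance of no responder among m participants is 0.95^m: 12.9% for m = 40, 35.8% for 20, 59.9% for 10 and 73.5% for 6.

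**What Wald then does.** The limits are d ± 1.96 × sqrt[p1(1-p1)/n + p2(1-p2)/m]. With p2 = 0 the second term vanishes and m drops out. For 4/12 with no placebo responders:

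- SE = sqrt(0.3333 × 0.6667/12) = 0.1361, and 1.96 × 0.1361 = 0.267.
- The interval is 33.3 ± 26.7, or 6.7 to 60.0 points, whether the placebo arm has 12, 6 or 3 participants.

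More generally, with 4 responders among n and none on placebo, the Wald lower limit is (4 - 3.92 × sqrt(1 - 4/n))/n. This is above zero for every n of 4 or more.

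**Comparison with Newcombe,** which combines the Wilson limits of each arm. For 4/12 vs 0/6 the Wilson limits are 13.8 to 60.9 and 0 to 39.0. The lower limit is 33.3 - sqrt[(33.3 - 13.8)² + (39.0 - 0)²] = 33.3 - 43.6 = -10.3, and the upper limit is 60.9.

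| Result | Wald (points) | Newcombe (points) |
|---|---|---|
| 4/12 vs 0/12 | 6.7 to 60.0 | 2.2 to 60.9 |
| 4/12 vs 0/6 | 6.7 to 60.0 | -10.3 to 60.9 |
| 4/12 vs 0/3 | 6.7 to 60.0 | -26.1 to 60.9 |
| 0/12 vs 0/6 | 0 to 0 | -39.0 to 24.2 |

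These rows depend on no assumed rate, so they apply to TVS as well as RECIST.

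**Coverage at 35% vs 5%,** by full enumeration. Misses at the lower and upper limit are nominally 2.5% each.

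| Size | Wald coverage | Lower / upper misses |
|---|---|---|
| 80/40 | 94.7% | 3.2 / 2.1 |
| 40/20 | 95.0% | 2.8 / 2.2 |
| 20/10 | 94.0% | 3.2 / 2.8 |
| 16/8 | 90.4% | 4.5 / 5.1 |
| 12/6 | 89.1% | 6.2 / 4.6 |
| 10/5 | 89.0% | 2.0 / 9.0 |
| 8/4 | 94.5% | 2.1 / 3.4 |
| 4/2 | 70.5% | 11.4 / 18.1 |

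The decline is uneven because counts are discrete. Newcombe and Miettinen-Nurminen stay between 96.5% and 98.2% at 20/10, 16/8, 12/6, 10/5 and 4/2.

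**Weak effect (assumed 10% vs 5%).** Wald coverage is 88.7% at 20/10, 86.3% at 16/8 and 76.3% at 12/6. At 12/6 the upper limit misses in 21.8% of cases, and zero-width bars make up 20.8 of those 21.8 points. Most of these arise when neither arm has a responder: 0.90^12 × 0.95^6 = 20.8%.

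**The case against.** The strongest reply is that nothing inferential rests on these bars. They lie outside the hierarchy in SAP 9.10.1, and no decision rule or interaction test uses them. That stands, and it is why the point is minor.

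Second, no sparse subgroup is shown to exist. That also stands. Age 65 or over and prior imatinib/nilotinib are only examples that may be small, and at the planned rates Wald performs well at 40/20 and 20/10.

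Third, a zero-width bar is visibly degenerate, so most of the weak-effect misses would not deceive a careful reader. This is correct. The misleading case is 4/12 vs 0/3, where the bar looks ordinary.

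Fourth, the plan already has exact methods, and one could read SAP 9.10.5 as carrying them into the subgroups. The text does not say so, and where 9.10.2 and 9.10.3.1 address the subgroup plots they name Wald. Overall exact analyses and participant listings do not correct a plotted bar.

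A reader might also infer that Wald misleads in large subgroups with no effect, for instance 60/30 at 5% vs 5%. The plan's own rates do not support that scenario. At 35% overall, 80 × 0.35 = 28 vimseltinib responders are expected; 60 × 0.05 = 3 would come from that subgroup, leaving 25 responders among the other 20 participants. At 5% vs 5% the overall 80/40 interval would be affected just as much (91.3% coverage), so this would not be a subgroup problem.

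**Conclusion.** The point holds for the subgroup forest plots of RECIST ORR and TVS ORR, and is minor. The stated interval ignores the size of an arm without responders and has no width when neither arm has one. That follows from the formula alone.

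How often it matters depends on assumptions. At 35% vs 5%, coverage is near nominal down to about 20/10 and irregular below that, between 70.5% and 94.5% at the smaller sizes shown. For TVS the frequency is unknown, because the documents give no TVS planning rates.

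Two stronger readings are not supported. One is that the overall Wald interval is unsound: at the planned rates its coverage is 94.7%, and an exact interval accompanies it. The other is that the trial's error control or primary result is affected: the plots are descriptive, and no hierarchical test uses them.

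**What to change.** In SAP 9.10.2 and 9.10.3.1, replace the Wald interval in the subgroup forest plots with an unstratified Miettinen-Nurminen or Newcombe 95% CI, and print responders/n for each arm beside each bar. Leave the overall analysis and its exact interval as written. This is one phrase in each section and a standard procedure option.

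The cost is in the display. Averaged over random 2:1 splits at 35% vs 5%, Newcombe bars are wider by about 12% at 60 participants (38.7 vs 34.5 points), 21% at 24 (63.7 vs 52.6) and 28% at 12 (88.0 vs 68.5). They are also lopsided: at 12 to 60 participants the lower limit misses in 0.1% to 0.6% of cases and the upper limit in about 3.1% to 3.6%, against a nominal 2.5% each. At 60 participants Newcombe's upper-limit misses exceed Wald's (3.2% vs 2.5%). The subgroup bars would also use a different method from the overall Wald interval, which a footnote should state.
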